6.1 Analysis Populations

The population of "all screened subjects" comprises subjects who signed the informed consent (ICF).

6.1.1 Safety Population

The safety population comprises randomized subjects who have received at least 1 dose of the study drug.

6.1.2 Intent-to-Treat Population

The intent-to-treat (ITT) population is defined as subjects who were randomized to treatment.

6.1.3 Modified Intent-to-Treat Population

The modified intent-to-treat (mITT) population will be defined as all randomized subjects who received at least one dose of study drug and had no major protocol violations based on key inclusion and exclusion criteria defining the population of interest (i.e., defined as not meeting inclusion criteria number 3, 4, 5, or 6).

The per protocol (PP) population will include the subjects in the mITT population who do not haveAllakos Inc.Page 29 of 49Confidential

any major protocol deviations or violations and have received all 6 doses of study medication (see Section 6.3 for list of protocol deviations and violations).

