A sample size of approximately 55 evaluable subjects per treatment group will provide >90% power to demonstrate a statistically significant difference between lirentelimab SC and placebo SC in absolute change in UAS7. We hypothesized a mean difference of at least 8 between lirentelimab SC and placebo SC and a pooled standard deviation of 11. This calculation is based on results derived from the AK002-006 study and expected placebo response rates reported in previously published data in H1-AH refractory CSU.

Additionally, randomization of up to approximately 130 subjects (65 per treatment group) will further support the evaluation of safety and tolerability of lirentelimab SC.

Statistical Analysis

All subjects who receive study medication will be included in the Safety population for safety analysis. Subjects who are randomized and have received at least 1 dose of study medication will be included in the modified Intent-to-Treat (mITT) population for efficacy analysis. mITT subjects who have received all 6 injections of study drug and do not have major protocol deviations possibly interfering with the interpretation of efficacy and safety assessment will be included in the Per Protocol (PP) population.

When appropriate, summary statistics of number of non-missing values, mean, median, standard deviation, minimum, and maximum will be computed for continuous variables and summary statistics of number and proportion will be computed for categorical variables.

Two-sided 95% confidence intervals (CI) will be provided for the mean and proportion. No formal statistical inferences will be made for safety parameters. Safety data will be summarized for each treatment group.

Baseline for safety analysis is defined as the last observation before administration of the first dose of study drug. Baseline for efficacy endpoints derived from daily diary assessments will be based on the 7 days before administration of the first dose of study drug.

Subjects will be stratified at randomization based on omalizumab experience for the treatment of CSU (exposed/naïve) and UAS7 score (16–27 or 28–42).

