16.2 Analysis Populations

The **Safety population** is defined as all subjects who received study medication.

The primary efficacy analysis population is the **modified Intent-to-Treat (mITT) population**, defined as all randomized subjects who have received at least 1 SC injection of study medication.

The **Per Protocol (PP) population** is defined as mITT subjects who have received all 6 injections of study drug and do not have major protocol deviations possibly interfering with the interpretation of efficacy and safety assessment. The study statistician and study team will review protocol deviations to identify subjects to be excluded from the PP population analysis.

The mITT population will be used for all efficacy analysis, and the PP population will be used to evaluate sensitivity of the primary endpoint and secondary endpoints.

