TLF	Tables, listings, and figures		
ULN	Upper limit of normal		
UPDD	Urticaria Patient Daily Diary		
WHO	World Health Organization		
WHODD	World Health Organization Drug Dictionary		

Revision History

Version Date	Version Number	Brief Summary of Changes
03 November 2023	Version 1	Original document

1. Introduction

This is a Phase 2, multicenter, randomized, double-blind, placebo-controlled study to evaluate the efficacy and safety of lirentelimab administered via subcutaneous injection (SC) in omalizumab-naïve or exposed adult subjects with H1-antihistamine (H1-AH) refractory chronic spontaneous urticaria (CSU).

The statistical analysis plan (SAP) describes *a priori* the data and variables to be summarized or analyzed, including specifications of the analytical methods to be performed. This SAP supersedes the statistical analysis methods described in the clinical protocol except for the standard pharmacokinetic (PK) data analyses. Significant deviations/changes from the planned analyses described in this SAP will be identified, with justification, in the appropriate section of the clinical study report (CSR). The SAP is based on Clinical Study Protocol AK002-027 Amendment 3, dated 07 September 2023 (Global), Clinical Study Protocol AK002-027 Amendment 4, dated 23 September 2023 (US Only), and the associated electronic case report form (eCRF).

2. Study Objectives

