4.2 Target of Estimation

The estimand for the AK002-027 study estimates the effect of treatment, while considering treatment adherence and response. The estimand will provide an answer to the question that is crucial to individual subjects: "If I take this study medication as part of my treatment regimen, without adding any further drugs that may impact the underlying disease or exit the study prematurely, what improvement in CSU might be anticipated after 12 weeks?"

The sections below describe the attributes of the estimand consistent with the ICH E9 (R1) Addendum (FDA, 2021).

4.2.1 **Population Targeted by the Scientific Question**

The population targeted by the scientific question is defined via the inclusion and exclusion criteria as part of the study protocol. Subjects may be male or female and must have a clinical diagnosis of CSU as defined by the study inclusion criteria.

Allakos Inc.

Confidential

4.2.2 Variables of Interest (or Endpoint) to be Obtained for Each Subject that is Required to Address the Scientific Question

The primary endpoint to be obtained for each subject in this study to address the scientific question is change from baseline in UAS7 score at Week 12.

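### SAP 6.1.3 narrows the primary (mITT) population under the protocol's own label, without declaring the change or planning an analysis of all randomized, dosed subjects

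*SAP*

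**What the plan says.** Protocol Section 16.2 names mITT as the primary efficacy population, "defined as all randomized subjects who have received at least 1 SC injection of study medication". The synopsis agrees: "Subjects who are randomized and have received at least 1 dose of study medication will be included in the modified Intent-to-Treat (mITT) population". Section 16.2 also says: "The mITT population will be used for all efficacy analysis". Protocol deviations enter only with the Per Protocol set, whose members must have had all six injections and "do not have major protocol deviations possibly interfering with the interpretation of efficacy and safety assessment".

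SAP Section 6.1.3 keeps the name mITT but adds a condition. Besides having received a dose, a subject must have "had no major protocol violations based on key inclusion and exclusion criteria defining the population of interest", and the SAP specifies the violation as not meeting inclusion criterion 3, 4, 5 or 6. SAP Section 6.9.1 performs the primary analysis on this population, with PP as support. PP is a subset of the narrowed mITT.

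On precedence, SAP Section 1 says: "This SAP supersedes the statistical analysis methods described in the clinical protocol". On disclosure, it says: "Significant deviations/changes from the planned analyses described in this SAP will be identified, with justification", and places that statement in the clinical study report.

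**The concern.** One label now covers two populations. Someone reading the protocol and then the study report will see mITT in both and assume that the primary result includes everyone randomized and dosed. Under the SAP it does not.

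The SAP does not alert that reader. It has no section on changes from the protocol, and its revision history records only an original document. The reporting commitment covers departures from the SAP, so a change made between protocol and SAP falls outside it.

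The added condition is also loosely drawn. It refers to inclusion and exclusion criteria but names only four inclusion criteria. It does not say that the judgement may use only information from before randomization, although criterion 6 includes willingness to keep a stable antihistamine dose throughout the study.

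At stake is the analysis closest to the randomized comparison. If dosed subjects are removed after randomization, the report should show what the effect is with them kept in. No planned output does that.

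**Working it through.** **1. The sets compared**

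| Set | Randomized | At least 1 dose | Inclusion criteria 3–6 met | Primary or secondary efficacy table in SAP Appendix 2 |
|---|---|---|---|---|
| Protocol mITT (16.2, synopsis) | yes | yes | not required | none |
| SAP mITT (6.1.3) | yes | yes | required | yes |
| SAP PP (6.1.3) | yes | all 6 | required | yes |
| SAP Safety (6.1.1) | yes | yes | not required | none |
| SAP ITT (6.1.2) | yes | not required | not required | none |

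The SAP Safety population has exactly the membership of the protocol's mITT, but no primary or secondary efficacy table uses it. Table 14.1.3 and Listing 16.2.1.3 will show how many subjects were excluded and why. They will not show the treatment effect with those subjects included.

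**2. The plan's own power figure**

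Inputs (Protocol 16.1, SAP 3.4 and 5.9): difference 8, SD 11, 55 per arm, 1:1 allocation, two-sided alpha 0.05. With noncentrality 8 / (11 × √(2/n)) and 2n − 2 degrees of freedom, n = 55 gives 96.6% (96.8% by the normal approximation). The stated >90% is reproduced. At 65 per arm the power is 98.4%.

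**3. Power after the SAP's exclusions**

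The documents give no rate of failure on criteria 3–6, so 2, 5 and 10% are assumed. Of 130 subjects that is 2.6, 6.5 and 13. The remaining number per arm is 65 × (1 − p), and a further 10% loss multiplies this by 0.9.

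| Assumed share p | n per arm | Power | n per arm with 10% loss | Power |
|---|---|---|---|---|
| 2% | 63.7 | 98.3% | 57.33 | 97.1% |
| 5% | 61.75 | 98.0% | 55.58 | 96.7% |
| 10% | 58.5 | 97.4% | 52.65 | 95.9% |

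**4. Possible shift in the estimate**

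Take an unfavourable case: excluded subjects have no treatment effect and the rest have the design effect of 8. The all-dosed effect is then 8 × (1 − p), and the SAP's estimate exceeds it by 8p. The design standard error at 65 per arm is 11 × √(2/65) = 1.93.

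- 2%: 0.02 × 8 = 0.16 points, 0.08 SE
- 5%: 0.05 × 8 = 0.40 points, 0.21 SE
- 10%: 0.10 × 8 = 0.80 points, 0.41 SE

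A smaller gap in effect gives a proportionally smaller shift.

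**5. Cost of keeping these subjects, same assumption, SD held at 11**

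| p | Diluted difference | Power at 65 per arm: kept / excluded | Power with 10% loss: kept / excluded |
|---|---|---|---|
| 2% | 7.84 | 98.1% / 98.3% | 96.87% / 97.13% |
| 5% | 7.60 | 97.4% / 98.0% | 95.95% / 96.71% |
| 10% | 7.20 | 95.9% / 97.4% | 93.95% / 95.88% |

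The largest penalty is 95.88 − 93.95 = 1.93 percentage points, and power stays above 90% throughout.

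**The case against.** The SAP states its definition openly and says that it overrides the protocol's statistical methods, so there is no doubt which text governs. The narrower set can also be defended on the estimand. SAP Section 4.2.1 says: "The population targeted by the scientific question is defined via the inclusion and exclusion criteria as part of the study protocol", and Protocol Section 6 says the same in substance. On that view, a subject who fails criteria 3–6 is outside the target.

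The safeguards are real. Criteria 3–6 mostly describe status before randomization. Decisions on violations and exclusions precede release of the code (SAP 5.6, Protocol 17.4). Eligibility is assessed at each screening visit and on Day 1, and Protocol Section 9 requires a re-check immediately before the first injection. If no dosed subject fails these criteria, the two sets are identical. Protocol 17.4 also mentions exclusions from an ITT population, which might suggest that some were foreseen.

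Most of this stands as a limit on size: exclusions are probably few and the risk of bias is low. It does not remove the point. Precedence settles which definition applies, but it neither tells the reader that the population changed nor says why. The ambiguous line in Protocol 17.4 does not alter the explicit definition in 16.2. The estimand argument could justify the narrower set, but the SAP does not make that argument, and it would not explain why only four inclusion criteria count. Even a well-argued restriction would leave the protocol's comparison unreported.

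**Conclusion.** The concern holds and should be fixed. The SAP changes the primary analysis population under an unchanged name, does not declare it, and plans no primary or secondary efficacy analysis in all randomized, dosed subjects.

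The expected numerical effect is small: at most 0.80 UAS7 points (0.41 SE) across the assumed range, and no threat to the stated power. Those figures rest on an assumed exclusion share of 2–10% and a zero effect in every excluded subject. Neither is documented, and the upper end is unlikely given the repeated eligibility checks. The case rests on the mismatch in definitions and the missing analysis, which need no assumption.

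One limit applies. SAP Section 1 cites two protocol versions, a global Amendment 3 and a US-only Amendment 4. The comparison here is with the one protocol supplied.

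**What to change.** Preferred: in SAP Section 6.1.3, define mITT as all randomized subjects who received at least one dose, analysed as randomized, and use it for the primary analysis. Apply the criteria 3–6 exclusion only in PP, where SAP Section 6.3 already lists it as a deviation, or in a labelled sensitivity analysis.

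Minimum, if the sponsor wants the narrower set as primary: give it a different name, state before unblinding that it departs from Protocol 16.2 and why, and add one primary-endpoint table on all randomized, dosed subjects.

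Either option is SAP wording. No new population flag is needed, because the Safety population already has the required membership. The preferred option keeps a few ineligible subjects in the primary analysis, with the slight dilution shown above. PP still gives the result without them.

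A separate minor point, not part of this finding: criterion 6 asks for a stable antihistamine dose for at least a week before screening, while the Day -21 route admits subjects who are not yet stable. The sponsor should reconcile these passages before criterion 6 is used to classify violations.

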6.2 Disposition of Subjects

Subject demographics and reasons for screening failure will be summarized for screen-failed subjects. Subjects (n and %) who completed or discontinued from the study will be tabulated by treatment group and for both treatment groups combined. The primary reasons for study discontinuation will be included in the tabulation. The primary reasons may include, but are not limited to, any of the following:

- Subject withdrew consent
- Lost to follow-up
- Administrative reason
- Adverse event
- Investigator decision
- Failure to follow required study procedures
- Other

Subject disposition will be summarized for the ITT population. Subject counts for the Safety, mITT, and PP populations will be included in the table. A data listing for subject disposition will be presented for the ITT population.

6.3 **Protocol Deviations and Violations**

Protocol deviations will include, but are not limited to

- Non-compliance with scheduled study visit
- Non-compliance with study treatment
- Received prohibited medications (see Protocol Section 9.1)
- Any major violations of efficacy-related entry inclusion or exclusion criteria (defined as not meeting inclusion criteria number 3, 4, 5, or 6)
- Non-compliance with study assessment procedures

Subjects with major protocol deviations will be listed. The listing will include a brief description of the deviation, deviation category, and if applicable, study day when deviation occurred along with other pertinent information. If warranted by the sample size, subjects (n and %) with major protocol

Allakos Inc.

Confidential

deviations will be tabulated by treatment group and by deviation category.

Subjects who are excluded from the PP population will be listed with reasons for exclusion.

6.4 Demographics and Baseline Disease Characteristics

The demographic and baseline characteristics variables are described in Section 5.10.

Descriptive statistics for these variables will be presented for all populations, by treatment group, and both treatment groups combined. Continuous variables will be summarized with n, mean, SD, and median. Categorical variables will be summarized with n and % of subjects for each category for the mITT, and PP populations.

6.5 Medical History

Subject incidence (n and %) of medical history (and current medical condition before signing the informed consent document) will be tabulated by the Medical Dictionary for Regulatory Activities (MedDRA), version 21.0) System Organ Class (SOC) and Preferred Term (PT).

6.6 Electrocardiogram

A listing of electrocardiogram (ECG) overall interpretations at screening visit will be provided.

6.7 Pregnancy Test

A listing of pregnancy test results will be provided.

6.8 Treatments

6.8.1 Treatment Compliance

Summaries of treatment compliance will be based on the safety population.

The compliance with study treatment will be calculated as follows:

Treatment Compliance = (Number of study drug injections during exposure period) / (Number of planned study drug injections during exposure period) x 100%.

The treatment compliance will be presented by the following specific ranges for each treatment group: <80% and $\ge80\%$.

In addition, an overall compliance that includes adherence to treatment administration schedule and any interruptions will be included in the data listing.

6.8.2 **Prior, Concomitant, and Newly Initiated Medications**

Prior medications and concomitant medications will be extracted from the Prior/Concomitant Medication CRF. Medications taken prior to Study Day 1 will be considered as prior medications, medications taken on or after Study Day 1 will be considered as concomitant medications, and newly initiated medication refers to any medication with a start date \geq Study Day 1. Note that a Prior Medication may also be a Concomitant Medication if the start date is prior to Study Day 1 and the end date is on/after Study Day 1. Medications will be coded using the WHO Drug Dictionary (WHODRUG GLOBAL September 2022 release) for preferred term (PT) and Anatomical Therapeutic Chemical (ATC) classification.

Medications will be tabulated separately based on the Safety population. The number (n and %) of subjects taking at least 1 medication and the number (%) of subjects taking each medication at the preferred term level will be tabulated by ATC4, and PT. Subjects taking the same PT medication twice will only be counted once.

A subject data listing will be provided to include the reported medication name, the WHODD PT, ATC4, study day and pertinent subject information.

6.9 Analyses of Efficacy Endpoints

For all efficacy variables, the analysis will be comparison of lirentelimab SC and placebo SC groups. The following null and alternative hypotheses for the primary endpoint will be tested for lirentelimab SC group and placebo SC group:

H₀: No treatment difference between lirentelimab SC and placebo SC

H1: There is a treatment difference between lirentelimab SC and placebo SC

Omalizumab experience for the treatment of CSU (exposed, naïve) and UAS7 score (16–27, 28–42) will be the 2 stratification factors for subject randomization and will be accounted for in the statistical modeling for efficacy. In addition, if it is evident that the primary endpoint is confounded by baseline disease characteristics at study entry, then the primary efficacy analysis will be adjusted for the effects of these variables.

6.9.1 Analysis of Primary Efficacy Endpoint

The primary endpoint will be analyzed using analysis of covariance (ANCOVA) using the imputed data set described below. The synthesizing method will be used to combine the results from multiple imputations. The least square (LS) mean, standard error (SE), and 95% confidence interval (CI) for each treatment group and for the between group difference will be derived from the ANCOVA model

with treatment as factor, and baseline UAS7 score and omalizumab experience for the treatment of CSU (exposed, naïve) as covariates. The hypothesis test for the treatment effect will be carried out by the F-test.

For the analysis described above, missing data from subjects who prematurely discontinue the randomized treatment, initiate any treatment adjustments as outlined in Section 4.2.5 (e.g., use of prohibited or rescue medication), or missing daily PRO scores as described in Section 2.1 will be imputed using multiple imputation (MI) techniques. There are five steps in the MI process.

- 1) Check missing data patterns.
- 2) Impute non-monotonic or intermittent data until only monotone missing data remains.
- 3) Use monotone regression to impute monotone missing data and create multiply imputed data sets.
- 4) Run the primary efficacy analysis (ANCOVA using SAS PROC MIXED) on the multiply imputed data sets.
- 5) Use SAS PROC MIANALYZE to combine the efficacy output to get a single estimate from all the imputed data sets.

6.9.1.1 Step 1. Checking missing data patterns

For this study, the missing data patterns will be checked by treatment and visits (baseline to Week 12). There are 3 steps to this process:

Create dataset for efficacy measure including visits from baseline to Week 12

```
data mi_chk1; set datax;
where paramcd="UAS7" and baseline <= visit <=Week 12;
run;
```

Transpose dataset to display each visit as one column:

```
proc sort data = mi_chk1; by treatment id;
proc transpose data=mi_chk1 out=mi_chk2 prefix='';
by treatment id;
id avisitn;
var aval;
run;
```

Use PROC MI with the NIMPUTE=0 option to create the "Missing Data Patterns" table for the specified variables:

```
ods output MissPattern=missp;
proc mi data=mi_chk2 NIMPUTE=0;
```

by treatment; var visit0(i.e., baseline) – visit12 (i.e., Week 12); run;

6.9.1.2 Step 2. Impute non-monotonic/intermittent data until only monotone missing data remains.

Fill in the intermittent missing data using the following code.

```
proc sort data = mi_chk2; by treatment;
proc mi data=mi_chk2 seed=12345 NIMPUTE=50 out=MI;
  by treatment;
  mcmc impute=monotone;
  var Visit0 – Visit12;
  run;
```

6.9.1.3 Step 3. Use monotone regression to impute monotone missing data and create multiply imputed data sets.

```
proc sort data = mi; by _Imputation_;
proc mi data=mi out=mi_reg seed=54321 nimpute=1;
by _Imputation_;
var treatment Visit0 - Visit12;
class treatment;
monotone regression;
run;
```

6.9.1.4 Step 4. Run the efficacy analyses (PROC MIXED) on the multiply imputed data sets.

```
/** Recalculate change from baseline at Week 12**/
data UAS7 imputed;
 set mi reg;
 chg=Visit12-Visit0;
run;
proc sort data=UAS7 imputed out=UAS7 imputed1;
 by imputation ;
run;
/** ANCOVA by imputation **/
ods output diffs=diffs lsmeans=lsm;
proc mixed data=UAS7 imputed1 method=reml;
 by imputation ;
 class region omalizumab experience TREATMENT;
 model CHG= region omalizumab experience Visit0 TREATTMENT;
 lsmeans TREATMENT / diff;
quit;
```

ods output close;

6.9.1.5 Step 5. Combine estimates of the 50 PROC MIXED models to create an overall estimate and a relative efficacy score.

```
/** Combine LS Means (by treatment and difference) **/
data lsmdiff;
  set lsm diffs(in=d);
  if d then treattment='DIFF';
run;
proc sort;by TREATMENT;run;
/** Synthesized results **/
ods output ParameterEstimates=SYNDIF;
proc mianalyze data=LSMDIFF alpha=0.05;
  by TREATMENT;
  modeleffects ESTIMATE;
  stderr stderr;
run ;
ods output close;
```

The primary efficacy analysis will be performed on the mITT population. The PP population will be analysed as a supporting analysis.

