3.4 Determination of Sample Size

A sample size of 55 subjects per treatment group will provide >90% power to demonstrate a statistically significant difference between lirentelimab and placebo in achieving a reduction in UAS7. We hypothesized a mean difference of at least 8 between lirentelimab SC and placebo SC, and a pooled standard deviation of 11. This calculation is based on results derived from the AK002-006 study and expected placebo response rates reported in previously published data in H1-AH refractory CSU.

Randomization of up to 130 subjects (approximately 65 subjects per treatment group) is driven by the powering calculations, the likely dropout rate of up to approximately 10%, and will further support the evaluation of the safety and tolerability of lirentelimab SC.

4. Definitions

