5.9 Multiple Comparisons/Multiplicity Adjustment

To control for the family-wise type-I error rate, the following testing procedures will be implemented:

Test primary efficacy endpoint at 2-sided α =0.05 level.

- If p≤0.05 for primary endpoint, then reject the null hypothesis that lirentelimab SC is no different from placebo SC and accept the alternative hypothesis that lirentelimab SC is superior to placebo SC in improving UAS7 score.
- If p≤0.05 for primary endpoint, the hypothesis tests for the secondary endpoints will proceed in the prespecified order (see Section 2.2). If at any point during the analysis of the secondary endpoints, the statistical test is not significant at 2-sided α=0.05 level, the hypothesis testing procedure will stop. Lirentelimab SC will be deemed superior to placebo SC for all endpoints prior to the stop.

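### The primary multiple imputation omits omalizumab experience, a randomization stratum and ANCOVA covariate, and its pooling step sets no complete-data degrees of freedom

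*SAP*

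**What the plan says.** SAP 6.9.1 specifies an ANCOVA "with treatment as factor, and baseline UAS7 score and omalizumab experience" as its terms. It is run on multiply imputed data, results are combined across imputations, and treatment is tested by an F-test. The text names neither the predictors for the imputation nor a rule for the pooled degrees of freedom. SAP 6.9 adds that both randomization strata will be accounted for in the efficacy models. SAP section 1 places the SAP above the protocol's statistical methods, so the code in 6.9.1.1 to 6.9.1.5 is the only detailed specification of the primary imputation:

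- **Step 1** transposes the UAS7 values to one column per visit, by treatment and subject. No other variable is carried along.
- **Step 2** makes 50 imputations by MCMC, separately by arm, from Visit0 to Visit12.
- **Step 3** completes the monotone part by regression: "var treatment Visit0 - Visit12".
- **Step 4** models change on region, omalizumab experience, Visit0 and a variable spelled `TREATTMENT`; its CLASS and LSMEANS statements use `TREATMENT`.
- **Step 5** tries to relabel the difference rows ("if d then treattment='DIFF"), then sorts and pools by `TREATMENT` ("proc mianalyze data=LSMDIFF alpha=0.05"), with no `EDF=` option.

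**The concern.** An imputation model that omits an analysis covariate assumes that exposed and naive subjects in the same arm with the same UAS7 history have the same expected later scores. If exposure predicts both later UAS7 and intercurrent events, and the link with events differs by arm, the imputed values favour one arm. The amount imputed may exceed the dropout of up to about 10% assumed in SAP 3.4, because SAP 4.2.5 also sets scores to missing after added antihistamine, corticosteroid or immunomodulator use.

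Without `EDF=`, the pooled degrees of freedom follow a large-sample formula and can far exceed those of the ANCOVA itself, giving an interval that is slightly too narrow. The misspellings bear on whether the printed code delivers the between-group difference at all.

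**Working it through.** **1. The plan's own figure.** Inputs: "Test primary efficacy endpoint at 2-sided α =0.05 level" (SAP 5.9); "A sample size of 55 subjects per treatment group will provide >90% power", "We hypothesized a mean difference of at least 8 between lirentelimab SC" and "and a pooled standard deviation of 11" (SAP 3.4). SE = 11 × √(2/55) = 2.098; 8/2.098 = 3.814; 3.814 − 1.960 = 1.854; power = 96.8% (96.6% by noncentral t). The stated bound is correct. With 10% dropout, 55/0.9 rounds up to 62 per arm, which 65 covers.

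**2. Terms in each model.**

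| Term | 6.9.1 text | Step 4 code | Steps 2 and 3 |
|---|---|---|---|
| Treatment | yes | yes (misspelled) | yes |
| Baseline UAS7 (Visit0) | yes | yes | yes |
| Omalizumab experience | yes | yes | **no** |
| Region | **no** | yes | **no** |

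**3. Effect of the omitted stratum.** Simulation with sequential regression imputation: N = 130, 400 trials per setting, 25 imputations. Assumed: 30% exposed, a 6-point covariate effect, a true difference of −8. Mean estimates:

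| Setting | Missing | Without | With | Complete data |
|---|---|---|---|---|
| Missingness unrelated to exposure | 10% | −7.97 | −7.97 | −7.97 |
| Related to exposure, both arms | 11% | −8.02 | −8.03 | −8.03 |
| Related to exposure, both arms | 26% | −8.09 | −8.10 | −8.05 |
| Related to exposure, placebo arm only | 27% | −7.59 | −8.12 | −8.13 |

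The last shift is 8.12 − 7.59 = 0.53 point, about a quarter of the average SE of 2.0. A second simulation (300 trials, 15 imputations, 25% exposed, weekly scores with AR correlation 0.8 and SD rising from 6 to 11) concentrated events in exposed subjects on active drug. It gave −8.2 without the stratum, −7.9 with it and −7.8 with complete data. The bias shrinks the effect in one case and inflates it in the other.

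**4. Effect of omitting `EDF=`.** Let λ be the fraction of missing information (assumed), m = 50, and ν_com = 126 (130 subjects less four parameters: intercept, treatment, baseline, omalizumab experience).

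- Without `EDF=`: ν = (m − 1)/λ². At λ = 0.10, 49/0.01 = 4900, t = 1.9604.
- With `EDF=126`: ν_obs = (127/129) × 126 × 0.90 = 111.6; ν = 1/(1/4900 + 1/111.6) = 109, t = 1.9819.
- Width ratio: 1.9819/1.9604 = 1.011. The nominal 5% test has true size 5.25%.

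| λ | df without | df with | CI widening | True size |
|---|---|---|---|---|
| 5% | 19600 | 117 | 1.0% | 5.24% |
| 10% | 4900 | 109 | 1.1% | 5.25% |
| 20% | 1225 | 92 | 1.2% | 5.28% |
| 40% | 306 | 60 | 1.7% | 5.37% |

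**5. Effect of the Step 5 misspelling if the code ran that far.** PROC MIXED reports first level minus second. With placebo = 1 (the coding given for the MMRM in SAP 6.9.2), the 50 difference rows keep the placebo value of `TREATMENT` and are pooled with the 50 placebo LS means. With assumed LS means of −10 and −18, the simulated rows average −10.02 and +8.03, so the pooled value is (−10.02 + 8.03)/2 = −1.0. Its SE is 9.3 (95% CI −19.4 to 17.4), against a correct placebo result of −10.0 (SE 1.4). The intended difference, 8.0 (95% CI 4.1 to 12.0), is never produced.

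**The case against.** Several stronger readings are tempting, and the documents do not support them.

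- **That the imputation ignores the ANCOVA covariates.** It does not: baseline UAS7 is Visit0, and treatment is handled in both steps. One covariate named in the text is missing. Serial UAS7 up to the event also carries much of what omalizumab experience would add.
- **That omalizumab experience is known to predict the endpoint.** In the open-label study (protocol 2.3), percent change in UAS7 differed (−73.2% naive, −46.6% failure), but absolute change, the measure used here, was −13.9 and −14.0 in small groups unadjusted for baseline. This trial also excludes primary non-responders to biologics (protocol 8.5, criterion 3). The 6-point effect is an assumption.
- **That the omission moves a typical trial's estimate by 0.4 point.** At 15 imputations, fits with and without the stratum differ by 0.40 RMS, but rerunning the same model with new random draws gives 0.31. At the planned 50 the figures are 0.28 and 0.18, with means of −8.01 and −8.02. Most of that figure is Monte Carlo noise.
- **That omitting `EDF=` contradicts the text.** The text has no degrees-of-freedom rule, so this is a refinement.
- **That a wrong difference would be reported.** Step 4 should stop on the unknown `TREATTMENT` before Step 5 runs. SAP 6.9.1 requires the between-group difference, and SAP section 7 requires independent reprogramming with matching results, so a missing difference row would be noticed.

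What stands against this defence is that double programming finds typing errors, not specification choices. Two programmers following the same SAP would both omit the stratum and `EDF=`.

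**Conclusion.** The point holds as a modest, inexpensive improvement to the primary analysis. The imputation leaves out a stratum that the analysis model uses. The mean effect is 0.01 point or less when missingness is similar across arms, and about 0.3 to 0.5 point against a hypothesized 8 when intercurrent events depend on exposure in one arm only. Because the direction depends on which arm, the omission cannot be called conservative. These sizes rest on assumed exposed shares of 25% to 30%, the assumed covariate effect and the assumed missingness.

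Omitting `EDF=` narrows the interval by about 1% to 2% and puts the test at about 5.2% to 5.4% for missing information of 5% to 40% at N = 130. This matters only for a borderline result.

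The misspellings are corrections to make, not evidence that the reported result would be wrong. Region is a direct conflict between the text and the code of the primary model and needs a decision.

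**What to change.** Amend SAP 6.9.1 before database lock and unblinding:

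1. Carry omalizumab experience through the Step 1 transpose, or merge it back by subject. Without this, Steps 2 and 3 cannot use it.
2. Add it to the Step 2 variable list as a 0/1 variable, and to the Step 3 CLASS and VAR lists ahead of the visits.
3. Decide whether region belongs in the primary ANCOVA and make the 6.9.1 text and Step 4 agree. If it stays, add it to the imputation in the same way.
4. Add `EDF=` to PROC MIANALYZE, equal to the ANCOVA residual degrees of freedom: 126 without region, 125 with a two-level region, at N = 130. State the rule in the text.
5. Correct `TREATTMENT` and `treattment` so that the difference rows form their own BY group. The label must suit the variable's type: if treatment is numeric, a character label will not work.

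The cost is a few lines of text and code. Omalizumab experience is already recorded for stratification, so no new data are needed.
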